We will conduct a randomized, double-blinded, placebo-controlled trial to evaluate the efficacy and safety of continuous transdermal NTG for treatment of hot flashes. Peri- or postmenopausal women who report frequent hot flashes, are not using other clinical hot flash treatments, have no known history of coronary disease or multiple risk factors for coronary disease, and do not have contraindications to NTG therapy will be recruited from the San Francisco Bay area. Prior to randomization, women will be asked to record all hot flashes on a validated symptom diary over a 7-day period. They will then complete a brief, 3-day run-in period in which they will wear a 0.1 mg/hr transdermal NTG patch daily to confirm willingness to apply the patch and eliminate those with sensitivities to even low-dose NTG. Women who demonstrate an average of 7 or more hot flashes per day by their screening diaries, are successful in applying a 0.1 mg/hr patch daily during the run-in period, and meet all other eligibility criteria will then be randomized in equal ratios to daily use of transdermal NTG or placebo for 12 weeks.

Randomized participants will be started on a 0.2 mg/hr NTG (or identical-appearing placebo) patch daily, as the minimum dose previously found to produce at least a one-third decrease in hot flashes in the investigators' pilot study. Women will apply a new patch each night before going to bed, immediately after removing the old patch, and avoid patch-free periods that might interfere with development of tolerance. Women will return for follow-up at 1 week, and those who show no signs of hypotension or severe hypertension and are not already completely satisfied with the change in their symptoms will be increased to a 0.4 mg/hr NTG patch (or identical-appearing placebo) daily. Based on reassessment at 2 weeks, women may increase their NTG (or placebo) patch to 0.6 mg/hr for the remaining treatment period.

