F.1.6. Schedule of administration during treatment phase: At the baseline visit, women who successfully complete the run-in with 0.1 mg/hr NTG and meet all eligibility criteria will be assigned in a 1:1 ratio to start using a 0.2 mg/hr NTG or identical-appearing placebo patch for the treatment phase of the study. Women will again apply a new patch each night, directly after removing the old one, and avoiding patch-free episodes that could interfere with maintenance of nitrate tolerance. At a 1-week follow-up visit, those who report persistent hot flashes, do not have blood pressure <90/60 or >180/110, and pose no other major safety or tolerability issue will have their NTG (or placebo) dose increased to 0.4 mg/hr. Based on the 2-week follow-up visit, women with persistent hot flashes and no significant blood pressure, safety, or tolerability issue will have their dose increased to 0.6 mg/hr and remain at this for the remainder of the study. Women who report being completely satisfied on a dose lower than 0.6 mg/hr or who have major safety or tolerability issues will be permitted to remain on a lower dose.

F.1.7. Discontinuation of NTG/placebo after treatment phase: At the 12-week visit, participants will be asked to wean off NTG (or placebo) over the next 1 to 3 days, by decreasing their patch dose on a nightly basis before stopping NTG/placebo completely. Specifically, participants who are being weaned from the 0.6 mg dose of study medication will be instructed to switch to 0.4 mg for one day, then to 0.2 mg for one day, then to stop study drug altogether. Participants who are being weaned from the 0.4 mg dose will switch to 0.2 mg for one day before stopping medication altogether. Women who are taking the 0.2 mg (the lowest dose hypothesized to have a therapeutic effect) will simply stop study medication without any change in dose. Women will be given a last supply of NTG or placebo medication (one patch of each dose strength needed to complete the weaning). Participant and staff blinding will be maintained throughout the weaning process; for participants taking placebo, weaning will use placebo rather than active NTG patches. In the event that a participant develops a potentially severe adverse event such as chest pain during weaning, she will be directed to seek immediate emergency attention, just as she would during any other time point of the study.

F.2 Concomitant Interventions

F.2.1 Allowed interventions

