- Two resting blood pressure and heart rate measurements and orthostatic measurements will be obtained by a trained study coordinator during an in-person visit, or participants will be guided by the coordinator in obtaining these measurements at home during a video visit.
- Women who report no symptoms of hypotension or other safety issues, have blood pressures within acceptable parameters, and continue to report bothersome hot flashes will be asked to increase to the next higher dose patch (0.6 mg/hr for those previously on 0.4 mg/hr, or 0.4 for those previously on 0.2 mg/hr) or corresponding placebo. Those who are not eligible or who decline to increase their dose will be permitted to remain on a lower dose.
- Women who are not yet postmenopausal will be reminded to refrain from sexual activity or use barrier contraceptives; those who report unprotected sexual activity will be asked to provide a urine sample for pregnancy testing.
- Participants will be given a second hot flash diary and asked to record all hot flashes during the 7 days prior to their 5-Week Clinic Visit.
- An appropriate supply of study medication (or placebo) will be dispensed and participants will be asked to apply NTG or placebo patches on a nightly basis leading up to the 5-Week Clinic Visit

C. 3-Week Telephone Call (for women taking 0.6 mg/hr NTG (or placebo)

- If a participant was started on 0.6 mg/hr NTG (or placebo) at the 2-Week Clinic Visit, the study coordinator will call the participant 1 week later to discuss adherence, assess adverse events, and address questions.
- If a safety concern is raised by this call, the participant will be asked to come in immediately for an in-person or video-based visit (or directed to seek emergency medical attention, as appropriate)
- Participants will be reminded of when to start their next hot flash diary at least 7 days before the 5-Week Clinic Visit.

D. 5-Week Clinic Visit

- Approximately 5 weeks after randomization, women will have a follow-up visit, returning their study medication logs and any unused medication, as well as their second completed hot flash diary.
- Potentially severe side effects of NTG will be systematically assessed and recorded, and other unanticipated adverse events that are reported will also be documented according to standard protocols.
- Study coordinators will review medication diaries and tabulate unused patches to assess adherence and trouble-shoot barriers to adherence.

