Every effort will be made to assure that participants complete follow-up procedures and visits according to the study protocol. Participant contact information including address, phone number(s), fax number(s), and email address will be obtained at the Screening Clinic Visit. Study coordinators will also request contact information for two family members or friends who will be able to locate the participant. The study team will encourage retention by educating participants about the importance of the study, maintaining a friendly and efficient study clinic environment, and encouraging excellent staff-participant rapport. Participants who miss a visit will be contacted by the study coordinator to reschedule the visit and to provide assistance in completing the visit. Participants will also be offered gift cards with the return of each completed hot flash diary (\$25 at the Baseline Clinic Visit and 5-Week Clinic Visit, and \$50 at the 12-Week Clinic Visit).

H.2.8 Follow-up visit time windows

Suggested time windows for completion each of the post-randomization follow-up evaluations will be as follows:

| Follow-Up Assessment | Time Window |
|----------------------|-------------|
|----------------------|-------------|

| | |
|--|--|
| 1-week clinic visit | 7 (\pm 3) days after the baseline clinic visit (i.e., 4 to 10 days after the baseline visit) |
| 2-week clinic visit | 14 (\pm 3) days after the baseline clinic visit (i.e., 11 to 17 days after the baseline visit) |
| 3-week telephone call | 21 (\pm 3) days after the baseline clinic visit (i.e., 18 to 24 days after the baseline visit) |
| 5-week clinic visit | 5 weeks (\pm 6 days) after the baseline clinic visit (i.e., 29 to 41 days after the baseline visit) |
| 8-week telephone call | 8 weeks (\pm 6 days) after the baseline clinic visit (i.e., 49 to 63 days after the baseline visit) |
| 12-week clinic visit | 12 weeks (\pm 6 days) after the baseline clinic visit (i.e., 78 to 90 days after the baseline clinic visit) |
| 4-week post-discontinuation telephone call | 28 to 42 days after the 12-week clinic visit (or discontinuation of study medication) |

I. SAFETY ASSESSMENTS

I.1 Potential Risks and Protective Measures

I.1.1 Potential risks of study procedures

A. Potential risks associated with the therapeutic intervention (transdermal NTG) include:

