APPENDIX A: Summary of Measures and Procedures at Study Visits

| Measures | Telephone Screening | Screening Clinic Visit | Run-in period | Baseline Clinic Visit | 1-Week Clinic Visit | 2-Week Clinic Visit | 3-Week Phone Call (for 0.6 mg) | 5-week Clinic visit | 8-Week Phone Call | 12-Week clinic Visit | 4-Week Post-Discontinuation Phone Call |
|---|---------------------|------------------------|---------------|-----------------------|---------------------|---------------------|--------------------------------|---------------------|-------------------|----------------------|--|
| Brief telephone eligibility survey | X | | | | | | | | | | |
| Informed consent documentation | | X | | | | | | | | | |
| Sociodemographics questionnaire | | X | | | | | | | | | |
| Medical/reproductive history questionnaire | | X | | | | | | | | | |
| Blood and Urine Testing | | X | | | | | | | | | |
| Electrocardiography | | X | | | | | | | | | |
| Current medications inventory | | X | | | | | | | | | |
| Alcohol and tobacco use questionnaire | | X | | | | | | | | | |
| Height and weight measurement | | X | | | | | | | | X | |
| Resing blood pressure & heart rate | | X | | X | X | X | | X | | X | |
| Orthostatic blood pressure and heart rate | | X | | X | X | X | | X | | X | |
| 0.1 mg/hr NTG patch run-in period | | | X | | | | | | | | |
| Hot flash symptom diary return | | | | X | | | | X | | X | |
| Pittsburgh Sleep Diary | | X | | X | | | | X | | X | |
| Randomization to NTG or placebo | | | | X | | | | | | | |
| Review of adherence to patches | | | | X | X | X | X | X | X | X | |
| Patch dose escalation | | | | | X | X | | | | | |
| Weaning of NTG or placebo patches | | | | | | | | | | X | |
| Hot Flash Related Daily Interference Scale | | X | | | | | | X | | X | |
| Pittsburgh Sleep Quality Index | | X | | | | | | X | | X | |
| Menopause-specific Quality of Life | | X | | | | | | X | | X | |
| Generalized Anxiety Disorder – 7 | | X | | | | | | X | | X | |
| Center for Epidemiologic Studies Depression | | X | | | | | | X | | X | |
| Adverse events assessment | | | | X | X | X | X | X | X | X | X |

REFERENCES CITED

Avis, N. E., S. L. Crawford, G. Greendale, J. T. Bromberger, S. A. Everson-Rose, E. B. Gold, R. Hess, H. Joffe, H. M. Kravitz, P. G. Tepper and R. C. Thurston (2015). "Duration of menopausal vasomotor symptoms over the menopause transition." *JAMA Intern Med* **175**(4): 531-539.

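### Women raised from 0.2 to 0.4 mg/hr at week 2 get no scheduled contact for a nominal 21 days, against about 7 after every other increase, and F.1.6 and Section D omit that step

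*Combined protocol and SAP*

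**What the plan says.** The week-2 increase is described in three places.

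- **H.2.5.B (2-Week Clinic Visit)** gives the visit-level rule. Women without hypotension symptoms or other safety issues who "have blood pressures within acceptable parameters, and continue to report bothersome hot flashes will be asked to increase to the next higher dose patch", that is, "0.6 mg/hr for those previously on 0.4 mg/hr, or 0.4 for those previously on 0.2 mg/hr".
- **F.1.6** says that eligible women with persistent hot flashes at week 2 "will have their dose increased to 0.6 mg/hr and remain at this for the remainder of the study". It lets satisfied women, and those with major safety or tolerability problems, stay lower. It gives no step from 0.2 to 0.4 at that visit.
- **Section D** says that "women may increase their NTG (or placebo) patch to 0.6 mg/hr for the remaining treatment period", again with no other step.

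Women can still be on 0.2 mg/hr at week 2 because H.2.5.A lets those who were ineligible for the week-1 increase, or who declined it, stay there.

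The 3-week call is conditional: "If a participant was started on 0.6 mg/hr NTG (or placebo) at the 2-Week Clinic Visit", the coordinator telephones a week later about adherence, adverse events and questions. The Appendix A column carries the same limit ("3-Week Phone Call (for 0.6 mg"). If the call raises a safety concern, "the participant will be asked to come in immediately for an in-person or video-based visit", or she is sent for emergency care. The next contact scheduled for all women after week 2 is the 5-week visit, which H.2.8 places "29 to 41 days after the baseline visit".

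**The concern.** The same step, 0.2 to 0.4 mg/hr, is followed by a visit about a week later if taken at week 1, but by no scheduled contact for three weeks if taken at week 2. The late group can include women held back at week 1 for hypotension symptoms, blood pressure or another safety issue, so the slower follow-up may fall on women for whom prompt follow-up is most natural.

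G.1.3 has coordinators ask about severe headache, chest pain and syncope at each follow-up contact. Without a call, these women are first asked after a nominal 21 days, and anything found sooner depends on the woman making contact herself.

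The dosing text adds a second problem. A coordinator working from F.1.6 alone could take a woman on 0.2 mg/hr directly to 0.6, a rise of 0.6 − 0.2 = 0.4 mg/hr, where H.2.5.B allows 0.2 mg/hr.

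**Working it through.** **Inputs** (H.2.8, days after the baseline visit; the protocol calls the windows suggested):

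| Contact | Nominal day | Window |
|---|---|---|
| 1-week visit | 7 | 4 to 10 |
| 2-week visit | 14 | 11 to 17 |
| 3-week call | 21 | 18 to 24 |
| 5-week visit | 35 | 29 to 41 |

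**Formulas**

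- Nominal gap = nominal day of next scheduled contact − nominal day of increase.
- Shortest gap = earliest next contact − latest increase.
- Longest gap = latest next contact − earliest increase.

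**The plan's own figure.** H.2.5.C puts the call one week after the 2-week visit: 21 − 14 = 7 days. This agrees with H.2.8.

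**Gap after each scheduled increase**

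| Increase | Next scheduled contact | Nominal (days) | Range (days) |
|---|---|---|---|
| First 0.2 patch, baseline (day 0) | 1-week visit | 7 − 0 = 7 | 4 to 10 |
| 0.2 to 0.4, week 1 | 2-week visit | 14 − 7 = 7 | 11 − 10 = 1 to 17 − 4 = 13 |
| 0.4 to 0.6, week 2 | 3-week call | 21 − 14 = 7 | 18 − 17 = 1 to 24 − 11 = 13 |
| 0.2 to 0.4, week 2 | 5-week visit | 35 − 14 = **21** | 29 − 17 = **12** to 41 − 11 = **30** |
| 0.2 to 0.4, week 2, if called | 3-week call | 21 − 14 = 7 | 18 − 17 = 1 to 24 − 11 = 13 |

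**Blood pressure, separately.** The call includes no reading. After either week-2 increase the next scheduled measurement is at the 5-week visit: 35 − 14 = 21 days (12 to 30). The two week-2 groups therefore differ in scheduled questioning, not in blood pressure monitoring.

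**Dosing text side by side.** For a woman on 0.2 mg/hr at week 2 with persistent hot flashes and no safety or tolerability issue, H.2.5.B gives 0.4 and F.1.6, read literally, gives 0.6. F.1.6 and Section D can be read as describing the usual path from 0.4, which is probably what was meant, but neither says so.

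**The case against.** The strongest reply is that the limit to 0.6 mg/hr was deliberate. The summary of changes records the call, under both H.2.5 and H.2.8, as added for women started on 0.6 mg/hr at 2 weeks. An extra check at the top dose is coherent, and F.1.4 makes 0.6 the only dose that needs two patches at once. This stands: the restriction is compatible with H.2.5.B, and a reader who inferred a drafting slip would go beyond the text. What the protocol does not give is a reason for following the 0.2 to 0.4 step less closely at week 2 than at week 1.

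The second reply is that a day-7 call achieves little. I.1.1 says headache is most frequent in the first 24 hours and expects blood pressure effects to diminish within 12 to 24 hours. The call would miss that period. Late steppers must also pass the symptom, safety and blood pressure checks at week 2, and G.1.3 tells all women to report chest pain, syncope and other severe effects between visits. All of this stands and limits the benefit to earlier scheduled questioning and shorter recall.

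Three stronger readings are tempting, and the documents do not support them.

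- *That women prone to hypotension go unmonitored.* The wait for a blood pressure reading is the same 21 days after either week-2 step. The group also includes women who declined or had no bothersome hot flashes at week 1.
- *That the trial's comparisons are compromised.* One rule applies to both arms, and the outcome diaries, the power calculation and the dose analysis in K.4.2 do not depend on the call.
- *That the number affected can be taken from the pilot.* C.3 reports the dose at which women ended (eleven on 0.6, three on 0.4, three on 0.2), not how many stepped up late. It gives neither an estimate nor a bound.

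**Conclusion.** The point holds as a modest safety-schedule and wording issue. Under H.2.5.B, H.2.5.C and Appendix A, the week-2 step from 0.2 to 0.4 mg/hr is the only scheduled increase not followed by scheduled contact at about 7 days. The nominal wait is 21 days (12 to 30). F.1.6 and Section D omit the step, and F.1.6 taken literally conflicts with H.2.5.B.

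This rests on two assumptions: that H.2.5.B is the operative rule, and that visits fall within the suggested H.2.8 windows. The number of women concerned is unknown. Extending the call would cut the wait for adverse-event questioning from 21 days to 7. It would not bring forward a blood pressure reading, would not cover the first day after the increase, and would not change efficacy or power. The change is worth making because it is cheap, not because the present schedule is unsafe.

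**What to change.** 1. **Section D and F.1.6:** state that the week-2 increase is one step, *from 0.4 to 0.6 mg/hr or from 0.2 to 0.4 mg/hr*. The instruction in F.1.6 to stay on the new dose can remain, since Appendix A schedules escalation only at weeks 1 and 2.
2. **H.2.5.C, heading and first bullet, and the Appendix A column heading:** give the 3-week call to *every woman whose dose was increased at the 2-week visit*, on active drug or placebo.

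H.2.5.B needs no change. Nor does H.2.8, whose row for the call does not carry the 0.6 mg/hr limit.

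The cost is one extra telephone call per affected woman, of a kind coordinators already make, and wording edits in four places, which need IRB approval under M.1. No new visit, form or measurement is required. If the sponsor prefers to keep the call as a top-dose check, item 1 should still be done, and one sentence in H.2.5.C should give the reason for the limit.

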F.1.4. Active and run-in patch dosing: Because data from our pilot study suggest that doses of 0.2 mg/hr or higher are more likely to result in meaningful improvement in hot flashes (see Preliminary Data section), we will use only 0.2, 0.4, and 0.6 mg/hr dosages of NTG during the active phase of the trial. For logistical reasons, the 0.6 mg/hr dosage will be obtained through simultaneous use of a 0.2 and 0.4 mg/hr patch, rather than a 0.6 mg/hr patch. Additionally, a 0.1 mg/hr patch will be used during a brief 3-day run-in period prior to randomization, to eliminate women who are unable to self-administer and tolerate even the lowest dose of transdermal NTG.

F.1.5. Schedule of administration during run-in: During the brief run-in period, women will apply a 0.1 mg/hr NTG patch to their chest or any clean, dry, hairless area of skin on the body except the extremities below the knee or elbow. Women will self-administer this patch at home daily (removing the old patch each night and replacing it with a new patch) for 3 days. Women will also be advised to rotate the location of the patch on a nightly basis to minimize risk of skin reaction or breakdown. Those who report persistent or significant

headache, develop skin reaction, hypotension, or severe hypertension at the baseline visit, or are otherwise unable to apply patches daily during run-in, will not continue to randomization.

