Blood pressure will be closely monitored before and during NTG (or placebo) therapy (also see “Safety Assessments” section below). At in-person screening and baseline visits and at each in-person follow-up visit thereafter, participants will undergo two resting blood pressure measurements by trained coordinators using calibrated monitors. Additionally, orthostatic measurements of blood pressure and heart rate will be obtained. If visits are conducted by video with participants at home, trained coordinators will guide participants step-by-step and in real time in obtaining the above measurements using automated monitors distributed to participants in advance of the visit.

In the event that participants report blood pressure readings <90/60 or >180/110 in outside contexts despite normal readings in the study visit, or participants report symptoms suggesting hypo- or severe hypertension despite normal blood pressure readings in the study visit, they will be invited to undergo additional home or ambulatory blood pressure monitoring for more intensive assessment of blood pressure.

B. Severe anticipated side effects of NTG therapy

At each follow-up visit or phone call after initiation of NTG or placebo, blinded study coordinators will systematically assess for the following potentially severe side effects of NTG therapy: 1) headache severe enough to interfere with instrumental activities of daily living; 2) chest tightness or pain interfering with instrumental activities of daily living, and 3) syncope (fainting or loss of consciousness). If reported, these symptoms will be recorded on adverse event forms that will indicate date of onset, date of resolution, likelihood of relationship to treatment, actions taken in response to the event, and severity according to the Common Terminology Criteria for Adverse Events (CTCAE) scale from the National Cancer Institute (National Cancer Institute 2009) (see “Safety Assessments” section below). Participants will also be given the phone number for the study site and will be instructed to contact study staff in between study visits to report any chest pain suggestive of cardiac ischemia, syncope, or other severe anticipated side effects such as headache interfering with daily activities.

C. Unanticipated adverse events

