Follow-up visits will consist of a 1-week clinic visit, 2-week clinic visit, 5-week clinic visit, 8-week telephone call, 12-week clinic visit, and 4-week post-discontinuation telephone call. These visits will be conducted by coordinators based at outpatient research facilities on the Mt. Zion campus of UCSF or in rented facilities in surrounding counties, or through secure video-based platforms.

A. 1-Week Clinic Visit

- Approximately 1 week after randomization, women will return for an in-person or video-based visit, bringing their study medication diaries and any unused medication.
- Potentially severe side effects of NTG will be systematically assessed and recorded, and other unanticipated adverse events that are reported will also be documented according to standard protocols.
- Study coordinators will review medication diaries and tabulate unused patches to assess adherence and trouble-shoot barriers to adherence.
- Two resting blood pressure and heart rate measurements and orthostatic measurements will be obtained by a trained study coordinator.
- Women who report no symptoms of hypotension or other safety issues, have blood pressures

within acceptable parameters, and continue to report bothersome hot flashes will be asked to increase to the 0.4 mg/hr NTG patch (or identical placebo) at this visit. Those who are not eligible or who decline to increase to 0.4 mg/hr will be permitted to remain on 0.2 mg/hr.

- Women who are not yet postmenopausal will be reminded to refrain from sexual activity or use barrier contraceptives; those who report unprotected sexual activity will be asked to provide a urine sample for pregnancy testing.
- An appropriate supply of study medication (or placebo) will be dispensed, and participants will be asked to apply NTG or placebo patches on a nightly basis leading up to the 2-Week Clinic Visit.

B. 2-Week Clinic Visit

- Approximately 2 weeks after randomization, women will return for an in-person or video-based visit, bringing their study medication logs and any unused medication.
- Potentially severe side effects of NTG will be systematically assessed and recorded, and other unanticipated adverse events that are reported will also be documented according to standard protocols.
- Study coordinators will review medication diaries and tabulate unused patches to assess adherence and trouble-shoot barriers to adherence.

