At all on-treatment interim follow-up visits (i.e., 1-week, 2-week, 5-week), transdermal NTG will be decreased or stopped in women with blood pressures <90/60 mm Hg (both measurements), or in those with blood pressures <100/60 mm Hg and symptoms such as dizziness that are suggestive of hypotension. Study medication will also be decreased or stopped in women with symptoms such as dizziness who have a resting blood pressure in the normal range but demonstrate orthostatic changes in blood pressure or heart rate when rising from the supine to standing position. These

women will also be given a standardized letter documenting their blood pressure reading to take to their regular health care provider to promote further monitoring and/or evaluation. In the event that there is a concern about the reliability of clinic measurements, or women report symptoms suggestive of hypotension despite having blood pressure measurements in the normal range, home-based or ambulatory blood pressure measurements will be obtained, to detect episodes of hypotension that may have been missed by clinic measurements. In the (hopefully unlikely) event that a participant reports a recent episode of syncope or loss of consciousness, study staff will also urge the participant to seek emergency medical attention.

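### The 3-week adverse-event call is limited to women started on 0.6 mg/hr, so a woman raised from 0.2 to 0.4 mg/hr at week 2 has no scheduled check until week 5

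*Combined protocol and SAP*

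**What the plan says.** Three parts of the protocol bear on this point.

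- **The main dosing path.** Under F.1.6, women start on 0.2 mg/hr, move to 0.4 at week 1, and at week 2 those with persistent hot flashes and no safety problem "will have their dose increased to 0.6 mg/hr and remain at this for the remainder of the study". Women may stay on a lower dose.
- **The late step.** At the 1-week visit (H.2.5 A), "Those who are not eligible or who decline to increase to 0.4 mg/hr will be permitted to remain on 0.2 mg/hr". At the 2-week visit (H.2.5 B) these women may then be raised, since the permitted increases include "or 0.4 for those previously on 0.2 mg/hr) or corresponding placebo".
- **The 3-week call.** H.2.5 C makes the call conditional on the top dose: "If a participant was started on 0.6 mg/hr NTG (or placebo) at the 2-Week Clinic Visit, the study coordinator will call the participant" a week later, to cover adherence, adverse events and questions. The column heading in Appendix A also restricts the call to 0.6 mg.

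The contacts that H.2.5 lists for all participants run from the 2-week visit directly to the 5-week visit. Nothing else in the protocol schedules a contact in between for a woman raised to 0.4 at week 2.

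**The concern.** As scheduled, every start or rise in dose is followed by a contact about a week later, with one exception: 0.2 to 0.4 mg/hr taken at week 2. The same step taken at week 1 is followed at week 2 by a full visit with blood pressure measurement.

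The women left out may not be a random subset. Some declined the week-1 rise because they were content with their symptoms. Others may have been held at 0.2 for a mild tolerability or safety problem. If such a woman has a persisting side effect on 0.4 and does not phone in, she is asked about it two weeks later than other newly escalated women. What is at stake is timely detection of side effects in a small group, not the validity of the efficacy comparison.

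**Working it through.** **Inputs.** Visit windows from H.2.8, in days after the baseline visit. Each reproduces from its nominal day and tolerance:

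- 1-week visit: 7 ± 3 = 4 to 10
- 2-week visit: 14 ± 3 = 11 to 17
- 3-week call: 21 ± 3 = 18 to 24
- 5-week visit: 35 ± 6 = 29 to 41

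**Gap from each dose step to the next scheduled adverse-event check.** Nominal gap = nominal day of check − nominal day of step. Shortest gap = earliest check − latest step. Longest gap = latest check − earliest step.

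| Dose step | Next scheduled check | Nominal (days) | Shortest (days) | Longest (days) |
|---|---|---|---|---|
| Start 0.2 at baseline | 1-week visit | 7 − 0 = 7 | 4 | 10 |
| 0.2 to 0.4 at week 1 | 2-week visit | 14 − 7 = 7 | 11 − 10 = 1 | 17 − 4 = 13 |
| 0.4 to 0.6 at week 2 | 3-week call | 21 − 14 = 7 | 18 − 17 = 1 | 24 − 11 = 13 |
| **0.2 to 0.4 at week 2** | **5-week visit** | **35 − 14 = 21** | **29 − 17 = 12** | **41 − 11 = 30** |

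The extremes assume that both contacts fall at opposite ends of their windows. For the 0.6 group, H.2.5 C times the call one week after the visit itself, so the practical spread should be narrower than 1 to 13 days.

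**Effect of extending the call to late 0.4.** The first check moves from the 5-week visit to the 3-week call: nominally 35 − 21 = 14 days earlier, with a range of 29 − 24 = 5 to 41 − 18 = 23 days.

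**Number of women.** The protocol does not give it. Each 1% of the planned 140 is 1.4 women. An assumed share of 1% to 10% gives 140 × 0.01 = 1.4 to 140 × 0.10 = 14 calls over the whole trial. As a rough outside figure, 3 of the 17 continuing pilot women stayed at 0.4 (C.3). If that share held in both arms and all of them reached 0.4 late, the count would be 140 × 3/17 ≈ 25. Since 0.4 is normally reached at week 1, the true number is likely to be well below that.

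**The case against.** The protocol nowhere says that each increase must be followed by a check at one week. The 1-week and 2-week visits apply to everyone, and the amendment summary introduces the 3-week call specifically for 0.6 mg/hr. That is the maximum dose and the only one worn as two patches (F.1.4), so a trigger tied to the top dose can be a deliberate choice.

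The expected yield is also low. By the protocol's account (I.1.1), headache is most frequent in the first 24 hours, tolerance is expected within 12 to 24 hours, and pilot headaches lasted less than a day on average. A day-7 call would mostly record effects that had already resolved.

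There are safeguards too:

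- A rise at week 2 is offered only to "Women who report no symptoms of hypotension or other safety issues, have blood pressures within acceptable parameters, and continue to report bothersome hot flashes", with orthostatic readings also taken at that visit.
- Hypotension at week 1 has its own rule in I.1.2: "At all on-treatment interim follow-up visits (i.e., 1-week, 2-week, 5-week), transdermal NTG will be decreased or stopped in women with blood pressures" below the stated limits. These women are already on the lowest active-phase dose, since "we will use only 0.2, 0.4, and 0.6 mg/hr dosages of NTG during the active phase of the trial", so they are unlikely to be candidates for a rise a week later.
- Under G.1.3 B, participants "will be instructed to contact study staff in between study visits to report any chest pain suggestive of cardiac ischemia", syncope or other severe effects, and G.1.3 C gives them a number for reporting any adverse event.

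These points limit the importance of the gap but do not explain it. The early timing of side effects, the option to phone and the checks before a rise apply equally, or nearly so, to women going to 0.6 and to women going to 0.4 at week 1, and both groups get a scheduled check at about a week. The status of 0.6 as top dose is a reason to keep that call. It does not explain why 0.4 is followed up at one week when started at week 1 but not when started at week 2. The week-2 checks are also done on 0.2, before exposure to the new dose.

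One limit stands in full. The call takes no blood pressure, so the interval without a scheduled reading from week 2 to week 5 is the same for the 0.6 group, and extending the call would not close it.

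**Conclusion.** The concern holds as a minor design point. One permitted dose rise, 0.2 to 0.4 mg/hr at week 2, has its first scheduled adverse-event check at nominally 21 days (12 to 30 within windows), against 7 days for every other start or rise. The arithmetic rests only on the H.2.8 windows, which the protocol calls suggested. The number of women affected is unknown and probably small, and no rate of persisting side effects at 0.4 is given, so the safety gain cannot be quantified. Adverse events are still elicited at week 5, and nothing here threatens the trial's conclusions.

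**What to change.** In H.2.5 C and in the Appendix A column heading, change the trigger for the 3-week call from starting 0.6 mg/hr to any dose increase at the 2-week visit. Keep the same questions and the existing rule that a safety concern on the call leads to an immediate visit or emergency referral. The H.2.8 window for the call names no dose and can stay. No dose or dosing rule changes.

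The cost is one short coordinator call per woman affected, about 1 to 14 calls in all under the assumed 1% to 10% share, plus IRB approval of the wording (M.1). The change adds an adverse-event and adherence check, but it does not replace a visit with blood pressure measurement.
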